5.3 ENROLLMENT AND RANDOMIZATION

There will be 18 participants per group (15 vaccine recipients and 3 placebo recipients). Investigators will be blinded to vaccine versus placebo within each group but not across groups. Participants will be block randomized. Group 1 (with a prime of Env-C Plasmid DNA IM alone at weeks 0, 4, 12) will be fully enrolled first. After the 18 participants in Group 1 are enrolled, the remaining groups, 2-7, will begin enrolling participants. Once 24 participants in Groups 2-7 have been enrolled (four from each group) and received their first vaccinations, enrollment and vaccinations in Groups 2-7 will be paused for the time it takes the PSRT to review (typically 3 to 14 days) blinded safety data from these 24 participants covering the period immediately after their first vaccination through Day 7. If it is determined to be necessary by the PSRT, the MHRP SMC will be consulted to review unblinded data to provide a recommendation on continuing enrollment.

When safety has been confirmed with PSRT review, the remaining 14 participants in each of Groups 2-7 will be enrolled, and vaccinations will continue until the first 24 participants in Groups 2-7 (four per group) have received their first boost dose (at 20 weeks—to create a time gap between boost vaccinations of the first cohort and the remaining study participants).

A second scheduled pause (this pauses boost vaccinations only; prime vaccinations can continue) will occur for Groups 2-7 after the same set of participants reviewed during the first scheduled pause (the first 24 participants (four per group) from Groups 2-7) has received its first boost (Group 1 can continue receiving vaccinations). This pause will review blinded safety data from these 24 participants, covering the period from the first boost through Day 7 after that boost. At both scheduled pauses, the PSRT will consult the SMC regarding the pause if either of the following conditions are met: 1) one (or more) participants experience an SAE that is related to a study agent, or 2) two (or more) participants experience grade 3 or 4 AEs of the same type (e.g. elevated ALT) related to a study agent. Boost vaccinations for Groups 2-7 will resume once safety data from the booster sentinel cohort have been reviewed by the PSRT and they have concluded it is safe to proceed.

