Design:	RV460 is an exploratory study that will assess the safety, tolerability, and immunogenicity of a vaccine regimen consisting of priming with an Env-C Plasmid DNA vaccine (with or without novel adjuvants) when given with or without adjuvanted HIV Env gp145 C.6980 protein vaccine and boosting with adjuvanted gp145 C.6980 protein with or without the gp120 DNA vaccine. The study will be carried out at the KEMRI/US Army Medical Research Directorate-Africa (USAMRD-A), Clinical Research Centre, Kericho; and 126 healthy adults will be enrolled. Participants enroll randomly into one of seven groups which have 15/3 vaccine/placebo recipients per group. Each participant will receive six injections (prime at week 0, 4, 12; boost at week 20, 32 and 56) followed up for a total of 108 weeks.
	Study objectives will be met by the testing of blood samples from all participants. Willing and eligible participants have the option to provide lymph node and mucosal secretion samples (semen, cervicovaginal, rectal), which will provide the data for objectives 2 and the sub-objectives.
Phase:	1
Population:	126 Healthy, HIV-uninfected male and female participants aged 18 to 40 years in Kericho, Kenya
Number of Sites:	1
Products:	
Env-C Plasmid DNA (HIV-1gp120 (93MW965.26) DNA)HIV Env gp145 C.6980 proteinDouble Mutant of Heat Labile E. coli enterotoxin (dmLT)ALF43: Army Liposome Formulation—43% Cholesterol*Aluminum Hydroxide Suspension—Fluid Gel (Rehydragel®)*

*From this point forward, Army Liposome Formulation—43% Cholesterol will be referred to as ALF43 and Aluminum Hydroxide Suspension—Fluid Gel will be referred to as Rehydragel®

Objectives:**Primary**

Exploratory study to assess the safety and tolerability (including reactogenicity) of Env-C Plasmid DNA given IM alone, admixed with ALF43 adjuvant, topically applied with dmLT adjuvant, or given with an adjuvanted HIV Env gp145 C.6980 protein and followed by adjuvanted HIV Env gp145 C.6980 boost IM vaccinations, with or without Env-C Plasmid DNA.

Secondary

Assess the immunogenicity of the various study vaccine combinations:

1. Determine whether the adjuvants under study improve the immunogenicity of the Env-C Plasmid DNA priming.
2. Determine whether the addition of ALF43 to the Rehydragel® –HIV Env gp145 C.6980 protein boost further improves the immune response to HIV Env gp145 C.6980 protein.
3. Determine whether adjuvants improve humoral responses across vaccination regimens.

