There will be 18 participants per group (15 vaccine recipients and 3 placebo recipients). Investigators will be blinded to vaccine versus placebo within each group but not across groups. Participants will be block randomized. Group 1 (with a prime of Env-C Plasmid DNA IM alone at weeks 0, 4, 12) will be fully enrolled first. After the 18 participants in Group 1 are enrolled, the remaining groups, 2-7, will begin enrolling participants. Once 24 participants in Groups 2-7 have been enrolled (four from each group) and received their first vaccinations, enrollment and vaccinations in Groups 2-7 will be paused for the time it takes the PSRT to review (typically 3 to 14 days) blinded safety data from these 24 participants covering the period immediately after their first vaccination through Day 7. If it is determined to be necessary by the PSRT, the MHRP SMC will be consulted to review unblinded data to provide a recommendation on continuing enrollment.

When safety has been confirmed with PSRT review, the remaining 14 participants in each of Groups 2-7 will be enrolled, and vaccinations will continue until the first 24 participants in Groups 2-7 (four per group) have received their first boost dose (at 20 weeks—to create a time gap between boost vaccinations of the first cohort and the remaining study participants).

A second scheduled pause (this pauses boost vaccinations only; prime vaccinations can continue) will occur for Groups 2-7 after the same set of participants reviewed during the first scheduled pause (the first 24 participants (four per group) from Groups 2-7) has received its first boost (Group 1 can continue receiving vaccinations). This pause will review blinded safety data from these 24 participants, covering the period from the first boost through Day 7 after that boost. At both scheduled pauses, the PSRT will consult the SMC regarding the pause if either of the following conditions are met: 1) one (or more) participants experience an SAE that is related to a study agent, or 2) two (or more) participants experience grade 3 or 4 AEs of the same type (e.g. elevated ALT)

related to a study agent. Boost vaccinations for Groups 2-7 will resume once safety data from the booster sentinel cohort have been reviewed by the PSRT and they have concluded it is safe to proceed.

Specific details of the randomization will be described in a separate randomization plan.

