2.5 STUDY DESIGN

The RV460 trial is an exploratory study that will assess the safety, tolerability, and immunogenicity of different adjuvant formulations in combination with an Env-C Plasmid DNA and HIV Env gp145 C.6980 protein in a prime-boost combination. Enrolled participants will receive 3 doses of Env-C Plasmid DNA as a prime (with or without adjuvants) or admixed with HIV Env gp145 C.6980 protein. The Env-C Plasmid DNA is given alone, formulated with the adjuvant ALF43 (Army Liposome Formulation with Monophosphoryl Lipid A (MPLA) and 43% Cholesterol) adjuvant, or co-administered with the transcutaneous adjuvant dmLT (*E. coli* heat labile enterotoxin) applied at the injection site. The HIV Env gp145 C.6980 protein boost will be mixed with ALF43, Rehydragel® or ALF43 plus Rehydragel®.

Study groups will be assessed for HIV-1 Env-specific antibodies responses elicited by boosting with HIV Env gp145 C.6980 protein adjuvanted with Rehydragel® with or without ALF43. Group 7 will assess whether or not the concept of co-delivery of Env-C Plasmid DNA and HIV Env gp145 C.6980 protein simultaneously will increase the frequency and magnitude of immune responses than Env-C Plasmid DNA given IM alone (after first three vaccinations – Study groups 1 and 2 or as an Env-C Plasmid DNA IM prime, protein IM boost combination as was observed in mice and non-human primates [18], [19, 92, 93].

Table 1: Study Design

Group	n =		Prime at weeks 0, 4, 12	Boost at weeks 20, 32, 56
	V	p		
1	15	3	Env-C Plasmid DNA (2 mg, IM)	HIV Env gp145 C.6980 protein (100 µg, IM)/Rehydragel® (500 µg, IM)

Group	n =		Prime at weeks 0, 4, 12	Boost at weeks 20, 32, 56
	V	p		
2	15	3	Env-C Plasmid DNA (2 mg, IM)	HIV Env gp145 C.6980 protein (100 µg, IM)/Rehydragel® (500 µg, IM)/ALF43 (200 µg, IM)
3	15	3	Env-C Plasmid DNA (2 mg, IM) + dmLT (50 µg, TCI)	HIV Env gp145 C.6980 protein (100 µg, IM)/Rehydragel® (500 µg, IM)
4	15	3	Env-C Plasmid DNA (2 mg, IM) + dmLT (50 µg, TCI)	HIV Env gp145 C.6980 protein (100 µg, IM)/Rehydragel® (500 µg, IM)/ALF43 (200 µg, IM)
5	15	3	Env-C Plasmid DNA (2 mg, IM)/ ALF43 (200 µg, IM)	HIV Env gp145 C.6980 protein (100 µg, IM)/Rehydragel® (500 µg, IM)
6	15	3	Env-C Plasmid DNA (2 mg, IM)/ALF43 (200 µg, IM)	HIV Env gp145 C.6980 protein (100 µg, IM)/Rehydragel® (500 µg, IM)/ALF43 (200 µg, IM)

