3.3 DOSAGE PREPARATION, DISPENSING AND ADMINISTRATION OF STUDY PRODUCT

The vaccines will be given by intramuscular (IM) injection into the deltoid muscle, excluding the dmLT adjuvant which is given by TCI. All products will be combined into one syringe (excluding dmLT) for IM injection, i.e., Env-C Plasmid DNA and HIV Env gp145 C.6980/ALF43A for study Group 7. Once combined, the vaccine regimen must be administered as soon as possible, although based on the stability data performed in our laboratory (data not shown but a comprehensive report was provided to DAIDS), all the vaccine formulations were stable for 24 hours. This is significantly more than required time to vaccinate a participant in the clinic. Alternating deltoids will be used for subsequent immunizations [63]. Vaccination in contralateral limbs has been successfully utilized to achieve prime boost in multiple vaccine trials [63]. Alternating sites allowed for better attribution of local reactogenicity reactions.

The site for injection cleaned with an alcohol wipe before the injection. Since the interventions are vaccines, the concept of a washout period does not apply. The duration of the interventions is unknown, but it is hoped that it would be ten years or longer.

See IB and Package Inserts for further information on each study product.

126 healthy men and women between the ages of 18 and 40 years will be randomized to one of seven groups:

Table 3: Study Groups

Group	N V/P	Prime at weeks 0, 4, 12	Boost at weeks 20, 32, 56
1	15/3	Env-C Plasmid DNA (2 mg, IM)	HIV Env gp145 C.6980 (100 µg, IM)/Rehydragel® (500 µg, IM)
2	15/3	Env-C Plasmid DNA (2 mg, IM)	HIV Env gp145 C.6980 (100 µg, IM)/Rehydragel® (500 µg, IM) / ALF43 (200 µg, IM)
3	15/3	Env-C Plasmid DNA (2 mg, IM) + dmLT (50 µg, TCI)	HIV Env gp145 C.6980 (100 µg, IM)/Rehydragel® (500 µg, IM)
4	15/3	Env-C Plasmid DNA (2 mg, IM) + dmLT (50 µg, TCI)	HIV Env gp145 C.6980 (100 µg, IM)/Rehydragel® (500 µg, IM) / ALF43 (200 µg, IM)
5	15/3	Env-C Plasmid DNA (2 mg, IM) / ALF43 (200 µg, IM)	HIV Env gp145 C.6980 (100 µg, IM)/Rehydragel® (500 µg, IM)
6	15/3	Env-C Plasmid DNA (2 mg, IM) / ALF43 (200 µg, IM)	HIV Env gp145 C.6980 (100 µg, IM)/Rehydragel® (500 µg, IM) / ALF43 (200 µg, IM)
7	15/3	Env-C Plasmid DNA (2 mg, IM) /HIV Env gp145 C.6980 (100 µg, IM)/ALF43 (200 µg, IM)	Env-C Plasmid DNA (2 mg, IM) /HIV Env gp145 C.6980 (100 µg, IM)/ALF43 (200 µg, IM)/Rehydragel® 500 µg, IM)

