4.4.2.2 Participant Replacement

Participants who withdraw, are withdrawn from this study, or are lost to follow-up after signing the informed consent form (ICF) and administration of the study product will only be replaced if enrollment is still open. If a participant withdraws from the study or discontinues vaccination before all slots have been filled, the vacated randomization slot will be filled with the next available participant.

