8.3 HALTING OR PAUSING RULES

8.3.1 NOTIFICATION OF AEs MEETING STUDY PAUSE CRITERIA

The PI notifies the PSRT, which includes the DAIDS MO, study chair, site PI, DoD research monitor or their designees within a few hours after the site is aware of the AE. The PSRT will convene within one business day to review these adverse events and determine disposition (including whether the SMC needs to review the event).

If a decision to resume study enrollment and study treatment administration is made, the PSRT and or SMC will record its judgment in a memorandum to the study file and notify DAIDS. The MHRP Clinical Operations Office (COO) will then forward the memorandum to the principal investigators and notify WRAIR IRB. As needed, the appropriate regulatory authorities will be informed in writing of the decision to resume or discontinue study activities. Kericho site is responsible for notifying KEMRI SERU and WRAIR IRB according to local standards and regulations. The sponsor (DAIDS) is responsible for notifying the FDA.

For SAEs, sites must also follow the DAIDS EAE Manual and submit the SAE to DAIDS Regulatory Support Center (RSC) Safety Office as soon as possible, but no later than 3 reporting days (as defined in the DAIDS EAE Manual v2.0), after the site's recognition that the event fulfills the criteria for SAE reporting.

For IND Safety Reports submitted to the FDA and received from DAIDS, the MHRP COO will complete the necessary reporting to WRAIR IRB, including telephone contact and a written report generated within 24 hours of the initial safety report. WRAIR HSPB will forward to the USAMRDC, ORP, HRPO.

If the trial is placed on an unscheduled safety pause, all enrollment and study agent administrations will be suspended until further notice. For the two scheduled safety pauses,

enrollments and vaccinations for Group 1 do not need to be paused; only Groups 2-7 would be affected. For any study pause or re-initiation after a pause, the study staff will contact the participants to inform them. If the study is on pause for vaccinations, safety blood work is continued per protocol. Vaccinations are resumed post-pause but those who have missed vaccine windows would resume based on consultation with the PSRT on a case-by-case basis based on the number of vaccinations missed, length of pause, etc.

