7: Pregnancy testing must be performed prior to vaccination and mucosal secretion collection

8: 9ml should be taken if CBC/Chem results not available on day of biopsy. Otherwise, 3ml should be drawn

9: Medically Attended Adverse Events will be followed through the end of the study, a full 12 months following the last vaccination

10: Participants will take home the diary card and complete and the diary card will be reviewed at 7 days after vaccination.

11: Additional testing as clinically indicated

12: A participant is considered enrolled into the study once they are randomized into a study group

13: Study vaccination outside of a participant's vaccination window may occur at the discretion of the PSRT.

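### Group 1 is filled before Groups 2–7 open, so it is randomised only between vaccine and placebo, contrary to the stated allocation to one of seven groups; specific optional contrasts using Group 1 are partly or wholly non-concurrent

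*Protocol*

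**What the plan says.** On allocation, the Protocol Summary (Design) and the Abstract both state: "Participants enroll randomly into one of seven groups which have 15/3 vaccine/placebo recipients per group". Section 3.3 repeats the claim for the whole sample: "126 healthy men and women between the ages of 18 and 40 years will be randomized to one of seven groups".

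On enrolment order, the Precis and Section 5.3 both state: "Group 1 (with a prime of Env-C Plasmid DNA IM alone at weeks 0, 4, 12) will be fully enrolled first". The next sentence in each is: "After the 18 participants in Group 1 are enrolled, the remaining groups, 2-7, will begin enrolling participants". Appendix A, footnote 12, makes enrolment and allocation the same event: "A participant is considered enrolled into the study once they are randomized into a study group".

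Two other places touch the order. Section 4.4.2.2 allows replacement while enrolment is open: "the vacated randomization slot will be filled with the next available participant". Section 8.3.1 says of the two scheduled pauses: "enrollments and vaccinations for Group 1 do not need to be paused; only Groups 2-7 would be affected".

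On use of the groups, Tables 5 and 6 in Section 7.2.1 pool Group 1 into the DNA-alone set (1+2), the Rehydragel-only boost set (1+3+5), all vaccine recipients (105) and all placebo recipients (21). Section 2.5 names as a comparator for Group 7 "Env-C Plasmid DNA given IM alone (after first three vaccinations – Study groups 1 and 2". Sections 7.2.2 and 7.2.3 permit, but do not require, comparisons between groups. Section 7.2.3 carries the safety groupings over to the Mann-Whitney tests of immune response and leaves room for others.

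**The concern.** The two descriptions cannot both hold. If Groups 2–7 open only once Group 1 is full, nobody entering during the Group 1 period can be allocated to another group, and nobody in the original fill of Groups 2–7 could have been allocated to Group 1. The only random step for Group 1 is vaccine or placebo.

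This matters for secondary objective 1 (adjuvanting the prime), secondary objective 2 (adding ALF43 to the boost) and the Group 7 question. For each, the natural comparator includes Group 1. A difference in calendar time, in who came forward early, or in assay run would then be mixed with the adjuvant effect, while the summary text tells the reader that allocation was random across all seven groups. One possible route is in Section 9.5: samples are shipped in batches as participants reach their timepoints, and Group 1 reaches each one first. Batch composition is not fixed, and testing the groups together would close that route.

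**Working it through.** **The plan's own figures.** N = 7 × (15 + 3) = 126, of whom 105 receive vaccine and 21 placebo. The Clopper-Pearson limits in Table 5 for the sets containing Group 1 reproduce: 6/30 gives 7.7–38.6%, 9/45 gives 9.6–34.6%, 4/21 gives 5.4–41.9%, 21/105 gives 12.8–28.9%. These descriptive intervals are not in question.

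**Group 1's share of each set** (Table 5):
- DNA alone (1+2): 15/30 = 1/2; sets 3+4 and 5+6: 0.
- Rehydragel-only boost (1+3+5): 15/45 = 1/3; set 2+4+6: 0.
- Comparator 1+2 for Group 7: 15/30 = 1/2; Group 7: 0.
- All vaccine: 15/105 = 1/7; all placebo: 3/21 = 1/7.

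**Bias.** Suppose everyone in Group 1 is shifted by d SD. A contrast is biased by d times the difference in Group 1 shares:
- Prime, 1+2 v 3+4 or 5+6: d/2.
- Boost, 1+3+5 v 2+4+6: d/3.
- 7 v 1+2: d/2 in size.
- 1+2 v pooled placebo: d(1/2 − 1/7) = 0.36d. 1+3+5 v pooled placebo: d(1/3 − 1/7) = 0.19d.
- All vaccine v all placebo: d(1/7 − 1/7) = 0.

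**Error rate.** Two-sided 5% Mann-Whitney test, normal data, 15 vaccinees per group, no true effect, 40,000 simulated trials:

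| d (assumed) | 1+2 v 3+4 | 1+3+5 v 2+4+6 | 7 v 1+2 |
|---|---|---|---|
| 0 | 4.8% | 5.2% | 4.8% |
| 0.1 | 5.3% | 5.2% | 5.0% |
| 0.25 | 7.2% | 6.5% | 6.4% |
| 0.5 | 14.3% | 11.4% | 10.8% |

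A second run of 20,000 trials gave 5.2/5.2/5.2%, 7.2/6.0/6.4% and 13.8/11.0/10.7% for the three non-zero shifts. The concurrent contrasts 2 v 3+4, 3+5 v 4+6 and 7 v 2 stayed at 4.4–5.1%. Testing Group 1 against Group 2 is a weak check for drift: it rejects in 9% of trials at d = 0.25 and 24% at d = 0.5.

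**Late refills.** If 3 of the 15 Group 1 vaccine places were refilled after the other groups opened (assumption), the bias falls only to (15 − 3)/30 = 0.40d for the prime and (15 − 3)/45 = 0.27d for the boost.

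**Precision of the concurrent rows.** SE in SD units = √(1/n₁ + 1/n₂). The difference detectable with 80% power is 2.80 × SE/√0.955, where 0.955 is the Mann-Whitney efficiency for normal data.

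| Contrast | SE, with Group 1 | SE, concurrent | Ratio | Detectable difference |
|---|---|---|---|---|
| Prime: 1+2 v 3+4, then 2 v 3+4 | √(2/30) = 0.258 | √(1/15 + 1/30) = 0.316 | 1.22 | 0.74 → 0.91 SD |
| Boost: 1+3+5 v 2+4+6, then 3+5 v 4+6 | √(2/45) = 0.211 | √(2/30) = 0.258 | 1.22 | 0.60 → 0.74 SD |
| Group 7: 7 v 1+2, then 7 v 2 | √(1/15 + 1/30) = 0.316 | √(2/15) = 0.365 | 1.15 | 0.91 → 1.05 SD |
| Prime after boost: 1+2 v 3+4, then 2 v 4 | √(2/30) = 0.258 | √(2/15) = 0.365 | 1.41 | 0.74 → 1.05 SD |

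**What the boost rows estimate.** Let b₀ be the ALF43 boost effect after a DNA-alone prime and b_A the effect after adjuvanted primes. The pooled contrast targets (b₀ + 2b_A)/3 and 3+5 v 4+6 targets b_A. They differ by (b₀ − b_A)/3.

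**The case against.** The order is stated plainly in the Precis and Section 5.3, and starting with the simplest prime is an understandable safety stagger. The comparisons are optional, unadjusted and hypothesis-generating; Section 7.2.2 says the study was not designed to detect safety differences. The pairings examined here are inferred from rows of a precision table. No passage shows a period shift, and large ones are less likely: one site, one set of eligibility criteria, cryopreserved samples and about 137 − 108 = 29 weeks of accrual. Randomisation detail goes to a separate plan, and Section 7.2.4 foresees a SAP, where labels and sensitivity rows ordinarily belong.

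Most of this stands and limits the point. It does not remove it: no randomisation plan or SAP can make allocation random between a group already filled and groups not yet open, and the three incorrect statements are in the protocol itself.

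Three stronger readings are not supported:
- A reader might infer that every pooled contrast containing Group 1 is compromised. All vaccine (105) v all placebo (21) is not, because every group is 15:3 and a Group 1 shift cancels.
- A reader might take Section 8.3.1 as a further conflicting account in which Group 1 is still enrolling at the pauses. It only exempts Group 1 from pausing, and a replacement under Section 4.4.2.2 would satisfy it.
- A reader might suppose that dropping Group 1 always leaves the same question. For the prime, 2 v 3+4 is clean only before week 20. Afterwards Group 2 has had ALF43 in the boost and Group 3 has not.

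**Conclusion.** The protocol claims random allocation across seven groups, a property its own enrolment order rules out. That part needs no assumption. Group 1 is a first cohort randomised 15:3 to vaccine or placebo; randomisation among groups can apply only to Groups 2–7.

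The affected comparisons, if made, are 1+2 v 3+4 or 5+6; 1+3+5 v 2+4+6; 7 v 1+2; 1+2 or 1+3+5 v pooled placebo; and Group 1 v any other group. The last is wholly non-concurrent and the others partly so. Unaffected are all vaccine v all placebo, vaccine v placebo within Group 1, contrasts among Groups 2–7, and single-group tabulations.

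The size depends entirely on an assumed shift: immaterial at 0.1 SD, modest at 0.25 SD, and two to three times the nominal error at 0.5 SD. The documents do not show that any result will be biased, only that randomisation does not protect these contrasts. The correction should be made; the design need not change.

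**What to change.** Keep the enrolment order.

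(a) In the Protocol Summary, Abstract and Section 3.3, say that Group 1 is enrolled first and randomised only between vaccine and placebo, and that randomisation among groups applies to Groups 2–7.

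(b) As a minor point, align the mention of Group 1 enrolments in Section 8.3.1 with Section 5.3, for example by saying it refers to replacements under Section 4.4.2.2.

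(c) In Section 7.2, to be carried into the SAP, label the affected contrasts as partly or wholly non-concurrent, leaving out all vaccine v all placebo. If they are made, show them beside a concurrent counterpart:
- prime before week 20: 2 v 3+4 and 2 v 5+6;
- prime effects after the boost: 2 v 4 and 2 v 6, which share the same boost;
- boost: 3+5 v 4+6;
- Group 7: 7 v 2.

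(d) State that 3+5 v 4+6 estimates the ALF43 boost effect only after adjuvanted primes, and keep the pooled contrast alongside. The only comparison after a DNA-alone prime, 1 v 2, is wholly non-concurrent.

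Cost: wording and a few table rows, with no change to enrolment, visits or samples. The added rows are less precise: standard errors are about 22% larger for the pre-boost prime and boost rows, 15% for 7 v 2, and 41% for 2 v 4 or 2 v 6 relative to the pooled prime contrast. The concurrent boost row also answers a narrower question.

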APPENDIX G. PARTICIPANT VISIT SCHEDULE

RV460/WRAIR #2672**Appendix G**
Participant Visit Schedule

Visit No.	Visit Day	Clinic visit activities	Optional Procedures	Approx. Time	Reimbursement
Screening	-45 to -3 days	Screening: Briefing & contact information, informed consents, test of understanding, medical history, vital signs, complete physical exam, 1 TBSP blood draw for: HIV test, hepatitis B and C, syphilis, general health, urine pregnancy test for women, urine test (dipstick) for blood and protein	-Pap smear for women who agree to vaginal secretion collection	4-5 Hours	1000 Ksh
1	0	Vaccination 1*: Enrollment & randomize, exam & eligibility review, vaccination or placebo, examine injection site 30-60 minutes post-injection, receive diary card, urine pregnancy test for women, 12 TBSP blood draw for: research tests & HIV	-Mucosal secretion collection	5 - 6 Hours	1000 Ksh (+1000 Ksh for each mucosal secretion collection)
Phone call or Clinic Visit 24-48 hours After Vaccination					1000 Ksh
2	3	Follow Up: exam & symptom review, review diary card, 2 TBSP blood draw for: research tests. Bring diary card.		2 Hours	1000 Ksh
3	7	Follow Up: exam & symptom review, review & collect diary card, 2 TBSP blood draw for: research tests. Bring diary card.		3 Hours	1000 Ksh
4	14	Follow Up: exam & symptom review, 5 TBSP blood draw for: general health & research tests		2 Hours	1000 Ksh
5	28	Vaccination 2*: Exam & eligibility review, vaccination or placebo, examine injection site 30-60 minutes post-injection, receive diary card, urine pregnancy test for women, 2 TBSP blood draw for: research tests		4 Hours	1000 Ksh
Phone call or Clinic Visit 24-48 hours After Vaccination					1000 Ksh

Visit No.	Visit Day	Clinic visit activities	Optional Procedures	Approx. Time	Reimbursement
6	35	Follow Up: exam & symptom review, Review diary card, 2 TBSP blood draw for: research tests. Bring diary card.		2 Hours	1000 Ksh
7	42	Follow Up: exam & symptom review, 4 TBSP blood draw for: research tests and general health. Urine pregnancy test for women that elect for optional procedure(s). Bring diary card.	-Mucosal Secretion collection	4 - 5 hours	1000 Ksh (+1000 Ksh for each mucosal secretion collection)
8	84	Vaccination 3*: Exam & eligibility review, vaccination or placebo, examine injection site 30-60 minutes post-injection, receive diary card, urine pregnancy test for women, 3 TBSP blood draw for: research tests		4 Hours	1000 Ksh

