Phone call or Clinic Visit 24-48 hours After Vaccination					1000 Ksh
9	87	Follow Up: exam & symptom review, review diary card, 2 TBSP blood draw for: research tests. Bring diary card.		2 Hours	1000 Ksh
10	91	Follow Up: exam & symptom review, review & collect diary card, 4 TBSP blood draw for: research tests. Bring diary card.		3 Hours	1000 Ksh
11	98	Follow Up: exam & symptom review, 9 TBSP blood draw for: general health, HIV & research tests. Urine pregnancy test for women that elect for optional procedure(s).	-Mucosal secretion collection -Lymph node biopsy	5 - 6 Hours	1000 Ksh (+1000 Ksh for each mucosal secretion collection & 5000 Ksh for lymph node biopsy)
Return in 1 week if lymph node biopsy was performed					
12	140	Vaccination 4*: Exam & eligibility review, vaccination or placebo, examine injection site 30-60 minutes post-injection, receive diary card, urine pregnancy test for women, 3 TBSP blood draw for: research tests		4 Hours	1000 Ksh
Phone call or Clinic Visit 24-48 hours After Vaccination					1000 Ksh
13	143	Follow Up: exam & symptom review, review diary card, 2		2 Hours	1000 Ksh

Visit No.	Visit Day	Clinic visit activities	Optional Procedures	Approx. Time	Reimbursement
		TBSP blood draw for: research tests. Bring diary card.			
14	147	Follow Up: exam & symptom review, review & collect diary card, 3 TBSP blood draw for: research tests. Bring diary card.		3 Hours	1000 Ksh
15	154	Follow Up: exam & symptom review, 9 TBSP blood draw for: general health, HIV & research tests. Urine pregnancy test for women that elect for optional procedure(s).	-Mucosal secretion collection	4 - 5 hours	1000 Ksh (+1000 Ksh for each mucosal secretion collection)
16	224	Vaccination 5*: Exam & eligibility review, vaccination or placebo, examine injection site 30-60 minutes post-injection, receive diary card, urine pregnancy test for women, blood draw for: 2 TBSP research tests		4 hours	1000 Ksh
Phone call or Clinic Visit 24-48 hours After Vaccination					1000 Ksh
17	231	Follow Up: exam & symptom review, review diary card, 3 TBSP blood draw for: research tests. Bring diary card.		2 Hours	1000 Ksh
18	238	Follow Up: exam & symptom review, 9 TBSP blood draw for: research tests, general health & HIV. Bring diary card. Urine pregnancy test for women that elect for optional procedure(s).	-Mucosal secretion collection	4 - 5 Hours	1000 Ksh (+1000 Ksh for each mucosal secretion collection)

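### Both scheduled safety gates are cut at Day 7, so release does not require the sentinels' first scheduled post-dose safety bloods (Day 14, and study Day 154 after the first boost)

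*Protocol*

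**What the plan says.** Protocol 5.3, repeated in the Precis, sets two scheduled pauses for Groups 2-7, both based on the same 24 sentinels (four per group). The first stops enrollment and vaccination while the PSRT reviews blinded data "covering the period immediately after their first vaccination through Day 7"; the review is expected to take 3 to 14 days. The second stops boosts only and uses data "covering the period from the first boost through Day 7 after that boost". At both, the PSRT must consult the SMC if one or more participants have a related SAE, or if two or more have "grade 3 or 4 AEs of the same type (e.g. elevated ALT) related to a study agent".

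Section 6.1.1.1 gives the safety panel as CBC, creatinine, ALT and AST, besides pregnancy and HIV testing. Appendix G says which visits carry it:

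- Day 3, and likewise study Day 143: "Follow Up: exam & symptom review, review diary card, 2 TBSP blood draw for: research tests".
- Day 7: "Follow Up: exam & symptom review, review & collect diary card, 2 TBSP blood draw for: research tests".
- Day 14: "Follow Up: exam & symptom review, 5 TBSP blood draw for: general health & research tests".
- Study Day 147 (7 days after the first boost): "Follow Up: exam & symptom review, review & collect diary card, 3 TBSP blood draw for: research tests".
- Study Day 154 (14 days after the first boost): "9 TBSP blood draw for: general health, HIV & research tests".

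**The concern.** A sentinel gate exists to reveal a safety problem before many more people are dosed. Here the data cut closes one visit before the first scheduled post-dose safety panel, at both gates. A symptomless liver, renal or blood-count change would be in the gate data only if a test had been clinically prompted or an early-dosed sentinel's Day 14 result had already arrived. The protocol's own example of a repeated AE, elevated ALT, is of the kind most likely to go unnoticed without a scheduled draw.

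The gates release 6 x 14 = 84 further participants, first to primes and later to boosts. Some of these regimens contain ALF43, which section 2.2.2 says has not been used in humans.

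**Working it through.** **1. Where the safety bloods fall.** Appendix A should settle this, but its CBC and chemistry rows lost their column alignment in the text available here. Its volumes are readable: the daily volumes sum to the stated cumulative total of 1889 mL. They split as follows (mL):

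- Days 3 and 143: 34 = 17 + 17. There is no room for a safety tube.
- Day 7: 23 = 17 + 6. Day 147: 40 = 34 + 6.
- Day 14: 77.5 = 42.5 + 17 + 6 + 6 + (3 + 3).
- Day 154: 126 = 68 + 34 + 6 + 6 + 6 + (3 + 3).

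The single 6 mL on Days 7 and 147 could be one antibody tube or CBC 3 + chemistry 3, so the volumes are not decisive. The placement rests on Appendix G, which labels those two draws research only.

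**2. How many sentinels lack the draw at release.** The Protocol Summary gives 108 weeks per participant and about 137 weeks to the last visit. Implied accrual is 126/(137 - 108) = 126/29 = about 4.3 per week. This average includes the first pause, so a range of 3 to 8 is also shown. Assume even sentinel dosing, t_i = (i - 1) x 7/r for i = 1 to 24, with the last sentinel dosed at T = 161/r days, and review starting at the Day 7 cut. Sentinel i is short of nominal Day 14 at time R if t_i + 14 > R.

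| r per week | T (days) | Short at the cut, T+7 | Short after 3-day review, T+10 | Short after 14-day review, T+21 |
|---|---|---|---|---|
| 3 | 53.7 | 3 | 2 | 0 |
| 4.3 | 37.1 | 5 | 3 | 0 |
| 6 | 26.8 | 6 | 4 | 0 |
| 8 | 20.1 | 8 | 5 | 0 |

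**3. New exposure in the gap.** After a 3-day review, release comes at T+10 and the last Day 14 draw at T+14. In those four days about 4 x 4.3/7 = 2.5 new participants are dosed (1.7 to 4.6 at 3 to 8 per week).

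**4. Boost gate.** The first released participant's boost is nominally due 140 days after release, at T+150 to T+161. The last sentinel's study Day 154 draw is at T+154. If the first review takes 7 days or more, nobody released is nominally due a boost before that draw.

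**5. Why not hold every vaccination for the laboratory results?** Moving the whole first pause by a week shifts release from T+10 to T+17, or from T+21 to T+28. The second dose is due on Day 28 +/- 7. Count sentinels whose nominal Day 28 falls after the pause starts at T and whose Day 35 passes before release. At 4.3 per week the count rises from 2 to 6 (3-day review) or from 9 to 13 (14-day review) of 24. If the last draw is on Day 17, the end of its window, the counts become 8 and 15.

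**The case against.** Several points on the other side stand.

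- Day 7 is a natural cut: it matches the solicited reactogenicity period in 8.1.1.1. Release is also a judgement that it is safe to proceed, not an automatic step.
- The PSRT watches data as they arrive, and 8.3.1 pauses the whole study on the same thresholds, so late results are still acted on. Section 8.4.1 also allows, but does not require, an SMC look three weeks after the 21st first boost.
- Section 2.2.3.3 reports no clinically significant laboratory abnormalities with ALF43's predecessor, so prior risk is modest.
- Holding all doses would be costly. Section 10.3.1 gives exceptions to the product schedule as an example of a major deviation, although 5.4 lets the PSRT permit out-of-window doses. Group 1 is not paused, so late second doses would fall only in Groups 2-7.

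These limit the size of the gap but do not close it, because none makes the laboratory results a condition of release. The last point governs the form of the fix.

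A reader might infer that the protocol contradicts itself by naming elevated ALT in a rule that cannot see ALT. It does not: a clinically prompted test, or an early sentinel's Day 14 result, can meet that rule. A reader might also infer that 84 people would be dosed with no laboratory data in hand. The calculation does not support that: at 4.3 per week, 21 of 24 sentinels have reached Day 14 even after the shortest review.

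**Conclusion.** The point holds as a modest design improvement. As written, neither gate requires any scheduled post-dose safety laboratory result. In practice the gap concerns the last-dosed sentinels after a short review: 3 of 24 (2 to 5) not yet at Day 14, and none after a 14-day review. The boost gate gains less.

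This rests on Appendix G for the placement of safety bloods, on even dosing at 3 to 8 sentinels per week, on nominal visit days, and on review starting at the cut. If a legible Appendix A showed CBC and chemistry on Days 7 and 147, the point would fall away; the volumes alone do not exclude that.

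**What to change.** In 5.3 and the Precis:

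- Keep the Day 7 PSRT review, and let the sentinels' own second doses resume after it, as now. Each follows that sentinel's own scheduled Day 14 bloods.
- State that first doses for the remaining 84 participants start only when the PSRT has also seen the Day 14 safety laboratory results of every sentinel who attended that visit.
- State that non-sentinel boosts in Groups 2-7 resume only when the PSRT has also seen the study Day 154 results of every sentinel who attended that visit.

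Leave the laboratory schedule alone. Adding a 6 mL panel at Day 7 would take the eight-week maximum in Appendix A from 444.5 to 450.5 mL, above the 450 mL limit in 5.5.

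Cost: wording in two places, with no extra blood or visits and no added second-dose delay for sentinels. After a short review the 84 start about 7 days later (T+17 instead of T+10, allowing three days to read the results), or T+20 if the last Day 14 visit is at the end of its window. After a 14-day review the draws have already been made.

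The earliest released participants carry a small risk of a slightly late first boost. If first doses start at T+17, their boost is due at T+157. A 14-day review counted from the last study Day 154 draw ends at T+168, which is 11 days after the due date and 4 days past the +7 window. The present text has the same worst case (T+161 against T+150). The sentinels' week-32 boost is unaffected.
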